Evidence of our experience successfully recruiting PAD participants for NHLBI-funded studies: In the past five years we have randomized > 463 PAD participants into NHLBI-funded clinical trials. In addition, since 1998, we have enrolled more than 1,800 men and women with PAD into our NHLBI-funded studies (R01-HL58099, R01-HL073351, R01-HL071223, R01-HL073912, R01-HL083064, and R01-HL089198). We have accomplished this using methods described above and by partnering with other Chicago medical centers.

C6. Randomization. Participants will be randomized to one of four arms using a SAS computer program (see Table 5). Participants will be stratified by diabetes mellitus, since patients with diabetes have fewer progenitor cells than those without diabetes (49,50). Based on our prior work, we anticipate that approximately 25% to 30% of participants will have diabetes (44). Block randomization will be implemented to ensure balance between the four groups throughout recruitment. Block sizes will be randomly selected from eight and twelve.

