hallway for six minutes after standardized instructions to complete as many laps as possible (44,81,85). Distance covered in six minutes is recorded. The intra-class correlation coefficient for the test-retest reliability of the six-minute walk test among 156 PAD participants in our SILC exercise trial was 0.90 ($p<0.001$) when two six-minute walk tests were completed one to two weeks apart (44).

C13. Treadmill testing. The Gardner graded treadmill exercise test is the standard, accepted treadmill protocol for measuring change in maximal treadmill walking time in response to interventions among PAD participants (82-84). The FDA requires treadmill evidence when evaluating therapeutic drugs for improving walking performance in PAD. In the Gardner exercise protocol, speed is maintained at 2.0 miles per hour (mph) and treadmill grade increases by 2.0% every two minutes (82-84). If patients cannot walk at 2.0 mph, treadmill speed is started at 0.50 mph and increased by 0.50 mph every 2 minutes until the participant reaches 2.0 mph, after which the treadmill grade is increased every two minutes.

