In our primary aim, we will determine at 12-week follow-up: (a) whether GM-CSF therapy combined with supervised treadmill exercise (Group A) significantly improves six-minute walk performance compared to GM-CSF therapy alone (Group B), (b) whether GM-CSF therapy combined with supervised treadmill exercise (Group A) significantly improves six-minute walk performance compared to supervised exercise therapy alone (Group C) and (c) whether GM-CSF therapy alone (Group B) significantly improves six-minute walk performance compared to placebo (Group D). We will also confirm the previously established association between supervised treadmill exercise (Group C) and improved six-minute walk performance, compared to no active therapy (Group D).

The final sample size in the PROPEL Trial, of 210 participants, was lower than the originally intended sample size of 240 participants. Prior to analyzing the data, investigators propose to alter the statistical analysis plan. The new statistical analysis plan allows us to address our original hypotheses but with greater statistical power, given the slightly lower sample size than originally intended. The revised statistical plan is as follows. The significance levels of the four primary comparisons will be determined using the Hochberg's step up method rather than the conservative Bonferroni correction. Specifically, we will sort the p-values from the smallest to the biggest as $p_{(1)} < p_{(2)} < p_{(3)} < p_{(4)}$. For the purposes of the analysis plan, the "hypothesis" refers to the null hypothesis. Rejecting all four hypotheses indicates that the hypotheses specified in our specific aims above are correct. Under this assumption, we will

- (1) reject all four hypothesis if $p_{(4)} \leq 0.05$;
- (2) otherwise, we will reject hypotheses (1-3), if $p_{(3)} < 0.05/2$;

- (3) otherwise, we will reject hypotheses (1-2), if $p_{(2)} < 0.05/3$;
- (4) otherwise, we will reject the hypothesis (1), if $p_{(1)} < 0.05/4$

The Hochberg's step up method also controls the family-wise type one error and is more powerful than the Bonferroni adjustment.

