C21. Statistical Analyses Methods. Change in six minute walking distance at 12-week follow-up is our primary outcome. Changes in brachial artery FMD, maximal treadmill walking time, and CD34+ cells at 12-week follow-up are secondary outcomes. The distributions of each outcome will be examined and appropriate transformations will be performed if necessary. Prior to the analyses, baseline characteristics (i.e., age, sex, race, baseline six-minute walk, ABI, CD34+ cells, and other relevant variables) will be compared between the four groups, using a F-test or Chi-Square test to ensure that baseline characteristics are balanced across the four groups. Any variables that are significantly different between groups will be adjusted for as covariates.

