For our Primary Aim, we will compare changes in six minute walk distance from baseline to 12-week follow-up between Groups A and B, between Groups A and C, between Groups B and D, and between Groups C and D using a two-sample t-test. Analysis of covariance will be used to adjust for baseline characteristics as necessary. For our Secondary Aim, we will compare changes in brachial artery FMD and maximal treadmill walking time from baseline to 12-week follow-up between Groups A and B, between Groups A and C, and between Groups B and D. We will also determine whether participants in Group C have greater increases in CD34+ cells at 12-week follow-up, compared to Group D. The two-sample t-test or analysis of covariance will be used for these comparisons. Efficiency augmentation methods for estimating the treatment effects using the distribution of baseline characteristics will be employed (96). The 95% confidence interval of the treatment effects will be constructed. Because the primary aim of the study is to demonstrate the superiority of Group A (GM-CSF + supervised exercise) as compared to Group B (GM-CSF alone) and Group C (supervised exercise alone), the commonly used two-way analysis of variance will be used only in supplementary analysis. Specifically, for the outcomes of interest in our primary and secondary aims, we will test the interaction between GM-CSF and supervised exercise with two-way ANOVA. In the absence of an interaction (i.e., the p value for the interaction term exceeds 0.25), we will further estimate the additive effect of GM-CSF and supervised exercise simultaneously in all 240 participants. Here, the existence of model-based additive effects for GM-CSF and exercise is much stronger than the targeted superiority of the combined treatments.

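### C21 does not fix which p-values enter Hochberg and admits baseline six-minute walk only through a chance-driven significance test; one always-adjusted primary analysis should be named

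*Combined protocol and SAP*

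**What the plan says.** All references are to the combined protocol and SAP.

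- **C21, primary test.** Change in six-minute walk is compared for A-B, A-C, B-D and C-D. The list of contrasts ends: "between Groups C and D using a two-sample t-test. Analysis of covariance will be used to adjust for baseline characteristics as necessary".
- **C21, covariates.** The four groups are first compared at baseline by F-test or chi-square, and then: "Any variables that are significantly different between groups will be adjusted for as covariates". No significance level is given. The list names six variables, baseline six-minute walk among them, and leaves room for others.
- **C21, augmentation.** After both the primary and the secondary comparisons comes: "Efficiency augmentation methods for estimating the treatment effects using the distribution of baseline characteristics will be employed (96" (the closing number is a literature reference). The outcomes covered, the covariates and the role of this analysis are not stated.
- **C20.** "The significance levels of the four primary comparisons will be determined using the Hochberg's step up method". The analysis that yields the p-values to be sorted is not named. The stated aim of the revision, made because 210 participants were reached instead of 240, is: "The new statistical analysis plan allows us to address our original hypotheses but with greater statistical power".
- **C6.** "Participants will be stratified by diabetes mellitus". Diabetes appears in no C21 model and is not among the six named variables.
- **C22.** With six-month drop-out expected below 10%, complete-case analysis backed by sensitivity analyses is judged sufficient. The next sentence brings in multiple imputation and pattern-mixture methods once drop-out passes 5%.

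**The concern.** A baseline test in a randomised trial detects chance imbalance. It does not detect whether a variable predicts the outcome, and prognosis is what makes adjustment worthwhile. Baseline walk is the obvious prognostic variable for change in walk, yet by this route it enters the model only when chance flags it.

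The unplaced augmentation sentence adds a second problem. Two competent statisticians could follow C21 and bring different p-values to Hochberg, one set from t-tests and the other from an augmented estimator. At stake are some power, in a plan reopened to recover power, and a unique primary result for each contrast.

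**Working it through.** **Figures in the plan.** C5 randomises 267: 240/(1 - 0.10) = 266.7, which rounds up to 267 and reproduces. C20 gives no effect size, SD or power, so there is no power figure to reproduce.

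**Inputs.** The baseline-to-12-week correlation rho is not given. C12 reports an intra-class correlation of 0.90, obtained "when two six-minute walk tests were completed one to two weeks apart". I take 0.90 as a ceiling and assume 0.8 and 0.7 as alternatives. Arms of 52 (4 x 52 = 208) treat the 210 as analysed.

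**Variance.** With equal variances at both visits, a change score has variance 2s²(1 - rho) and ANCOVA has residual variance s²(1 - rho²). The ratio is (1 + rho)/2, a saving of (1 - rho)/2. Single-contrast power, where the t-test has 80% at 0.05, is Phi(2.802/sqrt(ratio) - 1.960).

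**Hochberg simulation.** 60,000 four-arm trials per rho; bivariate normal walk distances; additive effects of 0.555 SD of change (t-test power 80% at 0.05); C20's thresholds; baseline test at an assumed 0.05.

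| | rho 0.9 | rho 0.8 | rho 0.7 |
|---|---|---|---|
| Variance ratio | 0.95 | 0.90 | 0.85 |
| 210/ratio (equivalent N) | 221 | 233 | 247 |
| Single-contrast power, adjusted | 82% | 84% | 86% |
| Mean Hochberg power, t-test | 74.7% | 74.5% | 74.5% |
| Mean Hochberg power, written rule | 74.8% | 74.8% | 75.0% |
| Mean Hochberg power, ANCOVA | 76.8% | 79.3% | 82.2% |
| Mean Hochberg power, augmented | 76.7% | 79.3% | 82.2% |
| Any verdict differs, t-test v ANCOVA | 19.8% | 27.1% | 33.2% |
| Any verdict differs, ANCOVA v augmented | 1.6% | 1.5% | 1.3% |
| Any verdict differs, t-test v written rule | 1.8% | 2.3% | 2.6% |
| Type I error per contrast, written rule | 4.9% | 4.8% | 4.7% |

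The written rule here has baseline walk as its only candidate covariate. If only exercise works, t-test and ANCOVA differ on some verdict in 15/22/27% of trials. A t-test and an augmented analysis can disagree only where the t-test and ANCOVA disagree or ANCOVA and augmentation disagree. Their disagreement therefore lies within 1.6 points of the t-test v ANCOVA row, for example 19.8 ± 1.6% at rho 0.9.

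**Six candidate covariates.** At an assumed 0.05 level with independent variables, at least one is flagged in 1 - 0.95^6 = 26.5% of trials. A separate simulation (3,000 trials per scenario, 210 participants) assumed correlations with change of -0.2 to -0.5 for baseline walk and 0.1 to 0.2 for the others, and standardised arm means of 0.9, 0.3, 0.6 and 0 for A to D. The written rule then differed from the t-test in 6 to 11% of trials. Under the null its family-wise error was 3.9 to 4.5%.

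**Stratum.** Let diabetes prevalence be p and its assumed effect on change be d SD. With q = p(1 - p)d² and R² = q/(1 + q), the actual level is 2[1 - Phi(1.960/sqrt(1 - R²))]. For p = 0.25 and 0.30 (the range in C6) this gives 4.81% and 4.79% at d = 0.3, and 4.49% and 4.44% at d = 0.5.

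**C22 trigger.** If 210 were randomised, more than 5% means at least 11 drop-outs. The binomial probability is 93.6% at the earlier exercise trial's 7.7% (C5) and 99.6% at the projected 10%. Drop-out lands above 5% and below 10% (11 to 20 participants) with probability 80% and 46%. These are six-month rates. C23 accepts late 12-week visits, so missing 12-week outcomes may be fewer; at assumed rates of 3/4/5/6% the trigger fires in 5/22/48/72%.

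**The case against.** C21 does contain a rule, and its reference to ANCOVA where needed can be read as pointing back to that rule. On that reading the procedure is defined apart from the significance level and the open list. The augmentation sentence may well be meant for the primary contrasts, in which case the proposed change gains no power. The only correlation the documents support gives about 2 points of power. The larger gains need assumed values, and the change is a further revision after the final sample size is known. All of this stands and limits the point.

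Three stronger readings are tempting but not supported.

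- **The 20 to 33% shows the damage done by the baseline-test rule.** It does not. It is the effect of moving from the t-test to an always-adjusted analysis, or of the unsettled choice between t-test and augmentation. The rule itself moves far fewer verdicts.
- **The plan inflates type I error.** The written rule does not. Picking the most favourable of t-test, full ANCOVA and selected-covariate ANCOVA after seeing the results would give 6.7 to 7.8% family-wise with prognostic covariates. Nothing in the documents says that such picking is planned, and C20 places its revision before the data are analysed.
- **C22 contradicts itself by replacing complete-case analysis.** It does not speak of replacement, and it pairs complete-case analysis with sensitivity analyses. Expecting less than 10% and acting above 5% can both hold. What is missing is which method is primary once the trigger fires.

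**Conclusion.** The point holds as an improvement worth making and as a gap in specification; it does not make the analysis invalid. C21 defaults to a less efficient test, lets chance decide on adjustment, and does not say whether augmented or unadjusted p-values go to Hochberg.

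The size depends on how augmentation is read. If it does not cover the primary contrasts, constant adjustment for baseline walk recovers the equivalent of 11 participants (221 - 210) at rho 0.90 and 23 to 37 at the assumed 0.8 to 0.7, against a shortfall of 30. If it does cover them, the benefit is only that the primary p-values become unambiguous. The figures assume normal data, equal variances at both visits, 52 analysed per arm and an effect chosen to give the t-test 80% power.

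The diabetes stratum is a note only: leaving it out makes the t-test at most slightly conservative under assumed effects, and C6 stratifies because of progenitor-cell levels, not walking. The C22 point is secondary. At the plan's own six-month rates the 5% trigger is the expected case, yet neither the governing time point nor the resulting primary method is stated. The binomial check treats 210 as randomised while the power work treats it as analysed. This matters little: at 240 or 267 randomised the trigger probability at 7.7% is still 93 to 95%.

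**What to change.** In C21:

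1. Delete the selection of covariates by baseline significance.
2. Make one ANCOVA, or one named augmented estimator, the primary analysis of all four 12-week contrasts, always adjusted for baseline six-minute walk and diabetes stratum.
3. State that its four p-values are the ones entered into Hochberg in C20.
4. Keep the unadjusted t-test as a sensitivity analysis.

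In C22, tie the missing-data rule to missing 12-week outcomes, reconcile the 10% and 5% statements, and name one primary method (for example multiple imputation), with the others as sensitivity analyses.

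The cost is a few sentences, little programming and no new data. Results are slightly less simple to present than a raw t-test. The change must be documented before analysis; the revision already described in C20 can carry it.

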For our Exploratory Aims, we will use linear mixed effects regression analyses to compare changes in six-minute walk performance, maximal treadmill walking time, and brachial artery FMD between baseline and six-week follow-up and between baseline and six month follow-up between Groups A and B, Groups A and C, Groups B and D, and Groups C and D. We will use linear mixed effects regression analyses to compare changes in progenitor cell measures between baseline and six-week follow-up and between baseline and six-month follow-up between Groups C and D. Outcomes measured at baseline and each follow-up visit will be longitudinal response variables in the regression model. The regression coefficients for the interactions between group indicators and visit time are parameters of interest. The subject specific random intercept will be used to incorporate the within subject correlations. For our Exploratory Aim #4, we will employ linear mixed regression analysis to evaluate the association between changes in CD34+ cells and other progenitor cell measures from baseline to two-week follow-up with changes in six-minute walk distance, brachial artery FMD, and maximal treadmill walking time between baseline and six-week, twelve-week, and six-month follow-up visits. The responses are longitudinally measured outcomes of change between baseline and the six-week, twelve-week, and six-month visits, respectively. The independent variables of interest are changes in CD34+ cells and other progenitor cell measures from baseline to two-week follow-up. We will employ similar linear mixed regression analysis to evaluate associations between changes in progenitor cells between baseline and six-week, 12-week, and six-month follow-up with changes in six-minute walk distance, brachial artery FMD, and maximal treadmill walking time during the corresponding time period. The responses are longitudinally measured outcomes of change between baseline and the six-week, twelve-week, and six-month visits, respectively. Independent variables of interest are changes in progenitor cells from baseline to six-week, 12-week, and six-month follow-up. Finally, we will perform regression analyses among participants randomized to

the exercise group to determine whether the degree of increase in lactate levels during exercise sessions is associated with the degree of increase in progenitor cells.

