C22. Intention to Treat. In all comparisons, we will employ the intention-to-treat principle. Participants will remain in their originally assigned groups for analyses, regardless of adherence to their assigned group. Based on our experience in our SILC clinical trial, the drop-out rate is expected to be <10% at six-month follow-up. Therefore, complete case analysis coupled with reasonable sensitivity analysis should be adequate to handle the problem of missing data. If the drop-out rate exceeds five percent, we will employ more sophisticated statistical methods such as multiple imputation and the pattern mixture approach to correct for the potential bias of estimates from simple complete-case analysis due to informative missing data. The study team has substantial experience employing these methods in prior studies (44,97,98). We will use the type one error value of 0.0125 to cope with multiple comparisons.

C23. Follow-up window. Follow-up testing will be completed within one week before or after the target follow-up date, at the 2-week, 6-week, 12-week, and 26-week follow-up time points after randomization. However, if the follow-up visit cannot be performed within the one week before or after the due date for each follow-up visit (e.g. if a participant is sick and unable to return to the center for testing within the follow-up window), we will obtain follow-up measures at any point up until the next scheduled follow-up test. For example, if we are unable to obtain the 12-week follow-up measures within the window, we will attempt to obtain the measures until the 26-week follow-up testing window begins.

D. HUMAN SUBJECTS.

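### A random intercept alone imposes one variance of change on every visit, so standard errors of the exploratory 6-week and 26-week comparisons can be wrong, probably modestly for the six-minute walk

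*Combined protocol and SAP*

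**What the plan says.** Section C21 of the combined protocol and SAP assigns linear mixed models to the exploratory aims. On the response it says "Outcomes measured at baseline and each follow-up visit will be longitudinal response variables in the regression model". On what is tested it says "The regression coefficients for the interactions between group indicators and visit time are parameters of interest". On dependence within a participant it says "The subject specific random intercept will be used to incorporate the within subject correlations". It mentions no random slope, serial correlation, unstructured covariance or robust standard error for these models.

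The contrasts are changes "between baseline and six-week follow-up and between baseline and six month follow-up between Groups A and B, Groups A and C", and likewise B against D and C against D. Progenitor cells are compared at the same two visits between C and D only.

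The visits are unequally spaced. C23 places them "at the 2-week, 6-week, 12-week, and 26-week follow-up time points after randomization". By Table 6, the walk, treadmill time and FMD are measured at 0, 6, 12 and 26 weeks, and progenitor cells also at week 2.

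On correlation, C12 reports: "The intra-class correlation coefficient for the test-retest reliability of the six-minute walk test among 156 PAD participants in our SILC exercise trial was 0.90", obtained "when two six-minute walk tests were completed one to two weeks apart". No correlation or SD of change is given for 6, 12 or 26 weeks. The 12-week primary and secondary comparisons use two-sample t-tests or analysis of covariance, not these models.

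**The concern.** A random intercept makes every pair of visits equally correlated. Change from baseline then has the same modelled variance at 6, 12 and 26 weeks, although the gaps differ more than fourfold. The fitted value is an average over visit pairs, so it can be too small for some visits and too large for others.

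The exposed visits are the ones tested. Under falling correlation the average is nearly right at 12 weeks, where these models are not the planned test, and least right at 6 and 26 weeks, where they are. Section B1 says the trial will help define when benefit peaks and how long it lasts. That account rests on the confidence intervals and p-values at these two visits.

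**Working it through.** The plan states no standard error or power for these models, so there is no figure to reproduce.

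**Inputs from the documents**
- Visits 0, 6, 12 and 26 weeks (Table 6, C23).
- Walk correlation 0.90 at one to two weeks (C12).
- Prior exercise trial, six-month walk change: +21.28 m (n=50) against -15.02 m (n=47), p<0.001 (Table 2).
- Pilot walk SDs by CD34+ tertile: 438, 347 and 268 ft, n=19 (C1c).
- Final sample 210 (C20), so 210/4 = 52.5 per arm.
- Type I error value 0.0125 (C22). I also show 0.05.

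**Assumptions:** visit time is categorical, data are complete, tests are two-sided and, in steps 2 and 3, variances are equal across visits.

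**1. What the model does.** With a random intercept and residual variance σ², Var(Y_t − Y_0) = 2σ² at every visit t. With complete data, the estimate of 2σ² is the average of Var(Y_s − Y_t) over all six visit pairs. With equal variances:

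model SE / true SE at visit t = √[(1 − mean ρ) / (1 − ρ_0t)]

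actual type I error = 2[1 − Φ(z × ratio)]

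Under constant correlation the ratio is 1.00 at every visit and nothing is wrong.

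**2. Bound on the 26-week walk correlation.**
- Difference: 21.28 + 15.02 = 36.30 m.
- If p<0.001 comes from an unadjusted t-test on 95 df, |t| ≥ 3.396, so SE ≤ 36.30/3.396 = 10.69 m.
- SD of change ≤ 10.69/√(1/50 + 1/47) = 52.6 m.
- Pooled pilot SD: √[(438² + 347² + 268²)/3] = 358 ft, or 109 m.
- ρ at 26 weeks ≥ 1 − 52.6²/(2 × SD²). This is 0.78 for SD 80 m (an assumed low value), 0.86 for 100 m and 0.88 for 109 m.

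**3. Falling correlation.** Take ρ(d) = 0.90·exp(−kd), with k set to reach the stated value at 26 weeks. The six lags are 6, 12, 26, 6, 20 and 14 weeks.

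| ρ at 26 wk | mean ρ | ratio wk 6 | ratio wk 12 | ratio wk 26 | wk 26 error, nominal 5% | wk 26 error, nominal 1.25% |
|---|---|---|---|---|---|---|
| 0.88 | 0.889 | 1.03 | 1.01 | 0.96 | 6.0% | 1.6% |
| 0.78 | 0.834 | 1.13 | 1.03 | 0.87 | 8.9% | 3.0% |
| 0.70 (outside the walk bound) | 0.788 | 1.19 | 1.03 | 0.84 | 9.9% | 3.6% |

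Example, first row at week 26: √[(1 − 0.8892)/(1 − 0.88)] = √(0.1108/0.12) = 0.961. With linear decay from 0.90 at 1.5 weeks to 0.78, the week-26 ratio is 0.856, a shortfall of 14%.

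**4. Other patterns.** Keep the base correlation constant and add between-participant variation in response, with variance v × 2σ².
- *Response appears by week 6 and persists.* Three of the six pairs include baseline, so the ratio at each follow-up visit is √[(1 + v/2)/(1 + v)]. This is 0.95 for v = 0.25 and 0.87 for v = 1: too small at both tested visits.
- *Response full at week 6, half at week 12, gone by week 26.* The average added variance is 2.75v/6 = 0.458v. The week-6 ratio is √[(1 + 0.458v)/(1 + v)], or 0.91 to 0.85 for v = 0.5 to 1. The week-26 ratio is √(1 + 0.458v), or 1.11 to 1.21. The direction reverses.

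**5. Check by fitting.** I used 150 REML random-intercept fits with 52 per arm, outcome SD 1, and exponential decay from 0.90 at 1.5 weeks to 0.70 at week 26. The model SE was 0.125 at every visit, against true values of 0.104, 0.121 and 0.152 at weeks 6, 12 and 26.

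**The case against.** The strongest reply is that the documents do not show that correlation falls. Their only walk correlation is at one to two weeks, and if it holds to 26 weeks the model is exact. That stands, and it rules out an unconditional claim.

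A reader might infer that the 26-week results are definitely anti-conservative and the 6-week ones definitely underpowered, because some arms decline while others train. That does not follow. Differences between arm means are absorbed by the group-by-visit terms. Only variation between participants within an arm changes the correlation. C10 also describes related cell-therapy effects present at four weeks and sustained at 24. If individual responses varied in that way, both tested standard errors would be too small.

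A reader might also expect a large effect on the walk. The prior trial's own result argues against it: with a walk SD of 100 m or more, the 26-week correlation is at least 0.86. This bound is itself soft. The pilot has 19 participants, the published p-value may be adjusted, and the bound covers the walk only.

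What the reply does not rescue is the specification. Nothing in the documents supports equal variance of change over unequal gaps, and nothing provides for checking or relaxing it.

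**Conclusion.** The point holds in conditional form. The stated model forces one variance of change on all visits. If correlation decays, standard errors are too small at 26 weeks and too large at 6 weeks; other response patterns make them wrong in other directions.

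For the walk, under decay, the 26-week shortfall is at most about 4% with an SD of 109 m and at most about 15% with 80 m. This rests on an unadjusted t-test in the prior trial, equal variances over time, and similar variability of change in this trial. For treadmill time, FMD and progenitor cells the documents allow no bound.

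It would go too far to say that the time course itself is distorted. With complete data the estimated changes are the same under either covariance, and only their error bars move. Nor are the trial's main conclusions at risk, since the 12-week primary and secondary tests do not use this model. The structure is worth correcting because a better one is readily available; the primary result does not depend on it.

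**What to change.** In C21, replace the random-intercept-only structure for the exploratory between-group comparisons with an unstructured within-subject covariance over the scheduled visits, treating visit as categorical and using Kenward-Roger degrees of freedom. State that robust (sandwich) standard errors will be used if that model does not converge.

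The cost is a sentence or two of SAP text and a changed model option. Four visits need 4 × 5/2 = 10 covariance parameters, and the five progenitor-cell visits need 5 × 6/2 = 15, against two for the random intercept. With "The final sample size in the PROPEL Trial, of 210 participants", that is easily supported. If correlation proves constant, little precision is lost.
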